### 6.2 Sample size

Due to the exploratory design no formal a priori hypothesis is defined. The intention is to learn more about the effect size of certain variables such as healing outcome when

3M 3M Deutschland GmbH [name] [name], Germany	Clinical Investigational Plan / Protocol  3M Confidential	CLIN-PROT-EU-05-293312 Version: 3 Status: Release Release Date: 01/30/2018 07:29:52 AM CST Page 22 of 60
--	---	---

compared to different local IAD care regimes in hospitals. The results of the study will be used to examine the feasibility of a potential subsequent confirmatory RCT.

Total: n = 60 patients

Stratum 1: n = 30 IAD 1A patients

(persistent redness without clinical signs of infection)

Stratum 2: n = 30 IAD 2A patients

(skin loss without clinical signs of infection)

The patients will be allocated 1:1 to either Cavilon Advanced Skin Protectant or hospital IAD standard care regime.

Each site is expected to recruit 10 IAD 1A and 10 IAD 2A patients for the study:

5 IAD 1A patients allocated to Cavilon Advanced Skin Protectant

5 IAD 1A patients allocated to hospital IAD care

5 IAD 2A patients allocated to Cavilon Advanced Skin Protectant

5 IAD 2A patients allocated to hospital IAD care

### **6.3 Level of significance and power**

Not applicable

### **6.4 Expected drop-out rate**

The sample size of 60 patients includes an anticipated drop-out rate of 20%.

### **6.5 Pass/Fail criteria**

Not applicable

### **6.6 Provision for interim analysis (if applicable)**

Not applicable

### **6.7 Termination criteria**

Termination criteria for the study are described under chapter 19.

 
3M Deutschland GmbH [name] [name], Germany
	
Clinical Investigational Plan / Protocol
 
3M Confidential
	
CLIN-PROT-EU-05-293312 Version: 3 Status: Release Release Date: 01/30/2018 07:29:52 AM CST Page 23 of 60

--	--	---

## 6.8 Deviations

A statistical analysis plan will be prepared for the study. The statistical analysis plan will be completed before data lock. Any deviation(s) from the statistical analysis plan will be described and justified in the final report.

## 6.9 Subgroup specification

Subgroups are specified with regard to different IAD severity categories.

IAD category 1A: persistent redness without clinical signs of infection

IAD category 2A: skin loss without clinical signs of infection

## 6.10 Procedures that take into account all the data

All data will be presented in individual patient data listings.

## 6.11 Procedures for accounting missing, unused or spurious data

Missing critical data about effects such as first time observation for 100% re-epithelialization of skin loss and complete healing of IAD without any signs of erythema will be imputed.

Patients excluded from any subset or per protocol analysis will be documented and justified.

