## 6. Statistical consideration

### 6.1 Statistical design, method and analytical procedures

This study is designed as an exploratory RCT to measure possible effects of Cavilon Advanced Skin Protectant in the management of IAD when compared to local IAD care regimes (please refer to the study endpoints for more details). The treatment will be integrated into the daily medical routine of the hospitals to assess the effects in comparison to the local IAD care under real-world circumstances.

All quantitative data such as demographics, IAD history, IAD skin assessments, pain assessments will be summarized with descriptive statistics. In general continuous variables will be summarized using the following standard descriptive summary statistics: number of observations, arithmetic mean, standard deviation, minimum, median, maximum. Categorical variables will be displayed by means of frequency tables and, where appropriate, shift tables. The statistical analyses will be based on analysis sets defined as follows:

Full analysis set including safety:

The full/safety analysis set will include all patients enrolled

Per-protocol analysis set:

The per-protocol analysis set – being a subset of the full analysis set – will only include patients who complete treatment of at least five days. Additionally, patients with major protocol violations which may have an impact on efficacy evaluation will be excluded from the per-protocol analysis set.

The determination of major protocol violations which may have an impact on the statistical analyses and the resulting definition of analysis sets will be performed prior to start of any statistical analyses. A summary of the number of patients per analysis set will be given and reasons for exclusion of a patient from an analysis set will be listed.

The statistical analysis will be performed using the software package SAS® version 9.3 or higher (SAS Institute Inc., Cary, NC 27513, USA).

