## 9. Patients

### 9.1 Inclusion criteria

Patients may be enrolled into this study if the answers to all these questions are yes.

1. Is the patient 18 years or older?
2. Has the patient or their legally authorized representative signed the Informed Consent Form?
3. Does the patient have IAD category 1A or IAD category 2A in the study area\*?
4. Is the patient incontinent and does stool and/or urine come into direct contact with the skin?
5. Is the patient able to be turned/positioned with regard to skin assessment and photo documentation?
6. Is there a reasonable expectation that the patient will remain in the hospital setting for at least 7 days?

\*NOTE: Study Area

The study area is defined as the sacral region going down to the upper thighs, bordered approximately 5 cm below the gluteal fold.

Study Area: IAD has to be present in this zone at the start of the study

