### **9.6 Expected duration of each patient’s participation**

The maximum duration of each patient’s participation is 21 days. If IAD heals before 21 days and the patient is still incontinent, the patient will stay in the study to assess IAD recurrence rate with continued application of the study device (Cavilon Advanced Skin Protectant) or in the case the patient is allocated to the local IAD care regime with products following the local

 
3M Deutschland GmbH [name] [name], Germany
	
Clinical Investigational Plan / Protocol
 
3M Confidential
	
CLIN-PROT-EU-05-293312 Version: 3 Status: Release Release Date: 01/30/2018 07:29:52 AM CST Page 32 of 60

--	--	---

IAD prevention regime. If IAD heals before 21 days and incontinence discontinued or incontinence constituents are not in direct contact with the skin anymore, the patient will be released from the study. Patients discharged from the hospital prior to 21 days fulfill the requirements for study completion and are not followed-up outside of the hospital. The maximum patient participation is 21 days. If IAD heals before 21 days and the patient is still incontinent, the patient will stay in the study in order to assess the IAD recurrence rate. The patient will continue treatment either with Cavilon Advanced Skin Protectant or the local IAD care regime depending on the assigned study arm. If IAD heals before 21 days and the patient is no longer incontinent (or incontinence constituents are not in direct contact with the skin anymore) the patient will be released from the study irrespective of allocation group. Patients that have completed at least 5 days, but terminate the study prior to 21 days i.e. due to hospital discharge, fulfill the requirements for study completion and are not followed-up outside of the hospital. Note: Any recurrence of IAD in both study groups is to be examined. If the hospital routinely does not use IAD prevention products, the recurrence of IAD is still to be observed for the group allocated to standard care. In this case, the study procedures of “Application: Comparator” and “Pain Score: Application” no longer apply (Appendix 24.1 B).

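### Time to healing (endpoint 4) will be right-censored, but the supplied plan gives no rule for patients who leave unhealed and does not limit its imputation to missed assessments

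*Combined protocol and SAP*

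**What the plan says.** Section 7.3 lists as endpoint 4 the time until the skin heals completely or the IAD category falls. Section 11.1 defines it as a number of days and gives no value for a patient who reaches neither.

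Observation is limited. Section 9.6 caps participation at 21 days and states: "Patients discharged from the hospital prior to 21 days fulfill the requirements for study completion and are not followed-up outside of the hospital". A second sentence there treats as completers "Patients that have completed at least 5 days, but terminate the study prior to 21 days i.e. due to hospital discharge". At entry the only requirement on length of stay is the question "Is there a reasonable expectation that the patient will remain in the hospital setting for at least 7 days" (section 9.1). Section 9.3 adds withdrawals, for example for a skin infection needing topical treatment. On drop-out, section 6.4 states: "The sample size of 60 patients includes an anticipated drop-out rate of 20" per cent.

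On analysis, section 6.1 says "In general continuous variables will be summarized using the following standard descriptive summary statistics" and lists count, mean, standard deviation, minimum, median and maximum. Its per-protocol set "will only include patients who complete treatment of at least five days", apart from major violators. Section 6.11 says of missing critical effect data that the "first time observation for 100% re-epithelialization of skin loss and complete healing of IAD without any signs of erythema will be imputed". Section 6.8 promises a SAP before data lock; it is not among the supplied documents.

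**The concern.** A patient discharged unhealed on Day 8 is a completer under section 9.6 and meets the five-day condition for the per-protocol set, yet has no healing time. All that is known is that healing would have taken more than eight days. The supplied text does not say what happens to that patient in endpoint 4.

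If the general summaries of section 6.1 are applied to the recorded times, such patients drop out. The slower-healing arm loses more of them, and what remains is its faster healers. The two arms then look more alike than they are.

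Section 5.1 says the study exists to learn effect sizes such as healing outcome and to judge whether a confirmatory trial is feasible. A compressed healing-time contrast would feed directly into that judgement. No formal test is planned, so what is at stake is a distorted estimate, not a false-positive rate.

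**Working it through.** **Figures in the plan.** Total 60, allocated 1:1, gives 30 per arm; two categories of 30 give 15 per arm in each. With 20% drop-out, 60 × 0.80 = 48, and 48 / 0.80 = 60, so the total is consistent. No stated figure bears on censoring itself.

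**What the documents say about healing.** Section 4.7 reports an uncontrolled study of this device: 4 of 4 patients with severe redness returned to normal skin, and 4 of 12 with skin loss re-epithelialized completely. It gives numbers of applications but no times in days and no comparator rates. The healing times below are therefore assumptions.

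**Assumptions.** Healing time is exponential with median m, so λ = ln 2 / m. There are three exit patterns, the same in both arms: (i) nobody leaves before Day 21; (ii) 20% leave uniformly over Days 5 to 21 and the rest stay; (iii) all leave uniformly over Days 7 to 21. The 20% in (ii) borrows the drop-out figure; the documents give no discharge rate. G(t) is the proportion not yet exited at time t if healing is ignored.

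**Formulas.**
- True restricted mean to Day 21: (1 − e^(−21λ)) / λ
- Share seen to heal: P = ∫ λe^(−λt) G(t) dt over 0 to 21
- Healed-only mean: ∫ t λe^(−λt) G(t) dt / P

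**Worked case, medians 7 and 14, pattern (i).**
- m = 7: λ = 0.0990, e^(−21λ) = 0.125, restricted mean 0.875 / 0.0990 = 8.84. Healed-only mean 10.10 − 21 × 0.125 / 0.875 = 7.10.
- m = 14: λ = 0.0495, e^(−21λ) = 0.354, restricted mean 0.646 / 0.0495 = 13.06. Healed-only mean 20.20 − 21 × 0.354 / 0.646 = 8.71.
- True gap 13.06 − 8.84 = 4.22 days. Healed-only gap 8.71 − 7.10 = 1.61 days, and 1.61 / 4.22 = 38%.
- Expected unhealed: 30 × 0.125 ≈ 4 against 30 × 0.354 ≈ 11 patients.

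**All patterns, by numerical integration.**

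| Medians (days) | True gap | Healed-only gap (i) | (ii) | (iii) |
|---|---|---|---|---|
| 7 and 14 | 4.22 | 1.61 (38%) | 1.54 (36%) | 0.97 (23%) |
| 8 and 12 | 2.49 | 0.95 (38%) | 0.90 (36%) | 0.57 (23%) |
| 7 and 21 | 6.31 | 2.20 (35%) | 2.10 (33%) | 1.33 (21%) |

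For medians 7 and 14, the unhealed shares are 12% and 35%, 16% and 39%, and 27% and 51% in the three patterns. The healed-only median gaps are 2.1, 1.9 and 1.1 days, against a true median gap of 7.

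**Does censoring repair it?** In a separate simulation with a true median of 14 days and 20% to 60% of patients discharged uniformly over Days 7 to 21, Kaplan-Meier gave medians of 14.1 to 14.2 days and the healed-only median was 6.5 to 7.5. Discharge was independent of healing in that simulation.

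**Null case.** If both arms have the same healing and the same stays, the healed-only summary creates no false gap.

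**The case against.** The strongest reply is that a healing that never happened is not missing data. Section 11.2 has the nurse record a category or IAD-free status every day, so an unhealed exit has an observed status, and the Day 04 to Day 19 photographs are kept as back-up. On that reading 6.11 covers missed assessments only. This is the more natural reading, and it stands. A reader might infer that 6.11 tells the analyst to assign healing dates to patients who never healed, which would make 100% of both arms healed. The wording does not exclude this, but the documents do not support it as the intended meaning.

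Nor does any sentence say that healing time will be summarised in healed patients only. Section 6.1 speaks in general terms, and endpoint 1 would show the unhealed share alongside. That too stands: healed-only is what the stated summaries give when no further rule is added. Showing the percentage healed reveals the problem but does not correct the time.

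Finally, a censoring convention for one of eleven unranked endpoints is often left to the SAP, and the individual listings (section 6.10) permit re-analysis. A reader might infer that the trial has no censoring rule at all; the documents cannot show that, since the SAP was not supplied. If the SAP is silent, however, any later survival analysis would be chosen with the data known.

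**Conclusion.** The point holds in a limited form. Right-censoring of endpoint 4 follows from the design, the supplied text has no rule for it, and the one imputation statement is not restricted to missed assessments. That statement bears on endpoint 4 because, for a category 2A patient, re-epithelialization is the fall in category.

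Summarised as written, healing time describes healed patients only. In the scenarios above the between-arm gap then shrinks to about 21% to 38% of the true restricted-mean gap. The shrinkage appears even when nobody leaves early, so it does not depend on a guess about length of stay. Its size does rest on exponential healing, on medians that are not in the documents, and on equal exit patterns in both arms. It illustrates the problem and does not predict the trial's result.

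Importance is minor to should-fix: there is no hypothesis, power target or pass/fail criterion to invalidate, and the SAP may already deal with it.

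**What to change.** In section 6.11 or the SAP, before data lock:

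1. Limit imputation to assessments missed while the patient is still under observation, using the first later daily assessment or back-up photograph that shows the event.
2. Assign no healing or re-epithelialization date to a patient never seen to reach it. Count that patient as not healed in endpoints 1 and 3, and censor endpoint 4 at the last in-hospital skin assessment.
3. Report endpoint 4 by Kaplan-Meier, by arm and within IAD category, with 95% confidence intervals.
4. Add one sensitivity analysis for informative exit covering section 9.3 withdrawals as well as discharges, for example counting unhealed exits as not healed by Day 21.

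Optional: a restricted mean to a pre-stated day, and separate reporting of the fall from category 2 to 1 and of IAD-free skin.

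The cost is wording and standard SAS procedures, with no new data. Three limits remain.

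- **Precision is low.** In pattern (iii) with medians 7 and 14, the restricted-mean difference to Day 14 (true value 10.10 − 7.57 = 2.5 days) has a standard deviation of 1.28 with 30 per arm and 1.80 with 15. The 95% half-widths are 1.96 × 1.28 = 2.5 and 1.96 × 1.80 = 3.5 days.
- **A median may not be reached.** Both Kaplan-Meier medians are reached in 81% (30 per arm) or 70% (15 per arm) of simulated trials in pattern (iii), and in 94% or 86% in pattern (ii).
- **Censoring assumes exit is unrelated to healing.** The analysis in item 4 tests this in one direction. In pattern (iii) it gives restricted means to Day 21 of 9.7 and 13.9, against true values of 8.8 and 13.1.

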## 6.12 Patient calculation per center

Each center is expected to recruit 20 eligible patients for the study (n = 10 IAD 1A patients; n = 10 IAD 2A patients). Depending on the recruitment rate the sponsor reserves the right to allow for competitive recruitment or to add additional centers. Each center includes at least 10 patients.

## 7. Design of the clinical investigation

### 7.1 Clinical investigational type

This is a multi-centre, multi-country, prospective, randomized controlled trial.

CE-marked study device will be used within the intended use according to the manufacturer's Instructions for Use.

 3M Deutschland GmbH [name] [name], Germany	Clinical Investigational Plan / Protocol  3M Confidential	CLIN-PROT-EU-05-293312 Version: 3 Status: Release Release Date: 01/30/2018 07:29:52 AM CST Page 24 of 60
--	---	---

## 7.2 Randomization and blinding

The random numbers will be generated by computer. The randomization is stratified with respect to two different IAD severity categories according to the Ghent Global IAD Categorization Tool [33; appendix 24.2]. Stratum 1 is defined as IAD category 1A (persistent redness without clinical signs of infection) and Stratum 2 as IAD category 2A (skin loss without clinical signs of infection). The strata are of same sizes (50:50 ratio). The participants will receive either Cavilon Advanced Skin Protectant or the local hospital IAD care products within the same stratum. Due to the obvious differences between the comparative hospital IAD care products and the study device, the study nurses cannot be blinded. A blinded assessor will assess the healing outcome based on the photographs of the study area that is defined as the sacral region going down to the upper thighs, bordered approximately 5 cm below the gluteal fold.

## 7.3 Endpoints

Due to the exploratory design of the study the endpoints are not divided into primary and secondary endpoints.

The following endpoints are defined for the study with regards to the comparison of Cavilon Advanced Skin Protectant and local IAD hospital care:

1. Number and percentage of patients completely healed (skin free of any IAD signs, including erythema)
2. Number and percentage of patients improved with regard to IAD category
3. Number and percentage of patients with 100% re-epithelialization of skin loss (skin loss: skin is moist, as the epidermal layer is missing)
4. Time to complete healing or reduction in IAD category
5. Protection of IAD category 1 patients from developing IAD category 2
6. Prevention with regard to IAD recurrence
7. Material cost based on product utilization such as type of products, frequency of application and days of treatment
8. Use of resources involved in the IAD therapy
9. Nursing time to clean up incontinence and to administer IAD treatment products
10. Pain scores with regard to cleansing procedure and application of IAD product (Wong-Baker FACES® Pain Rating Scale: assessment only for cognitively healthy patients according to the judgement of the study nurse)

 3M Deutschland GmbH [name] [name], Germany	Clinical Investigational Plan /  Protocol  3M Confidential	CLIN-PROT-EU-05-293312 Version: 3 Status: Release Release Date: 01/30/2018 07:29:52 AM CST Page 25 of 60
--	--	---

11. Number and percentage of patients with adverse events and the nature of each adverse event

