#### 18.1.2 Assessment of methods

Safety parameters defined for this study will be collected for all study participants beginning at Day 01 until the final study visit, or until the patient is discharged from the hospital. The Adverse Event Case Report Form will be used to capture any safety-related concerns (eCRF). Device deficiencies regarding Cavilon Advanced Skin Protectant will be documented on the Device Deficiency Form (i.e. quality complaints and near incidents). The Device Deficiency Form is stored in the Investigator Site File. All device deficiencies that led to any hazard for the patient have to be regarded as adverse device effect and are to be documented in the eCRF/Adverse Event Case Report Form.

 3M Deutschland GmbH [name] [name], Germany	Clinical Investigational Plan /  Protocol  3M Confidential	CLIN-PROT-EU-05-293312 Version: 3 Status: Release Release Date: 01/30/2018 07:29:52 AM CST Page 48 of 60
--	--	---

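### Endpoint 11 compares crude adverse event percentages although patients are observed for different lengths of time; observation days by arm and a rate or fixed-window figure should be shown beside them (low priority).

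*Combined protocol and SAP*

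**What the plan says.** Section 7.3 introduces its list this way: "The following endpoints are defined for the study with regards to the comparison of Cavilon Advanced Skin Protectant and local IAD hospital care". Item 11 is the "Number and percentage of patients with adverse events and the nature of each adverse event". Section 6.1 puts all enrolled patients in the full/safety analysis set and summarises categorical variables in frequency tables and, where appropriate, shift tables.

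Section 18.1.2 collects the safety parameters "beginning at Day 01 until the final study visit, or until the patient is discharged from the hospital". How long that lasts varies by patient:

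- **Upper limit.** Section 9.6: "The maximum duration of each patient’s participation is 21 days".
- **Discharge.** Patients who leave hospital early "fulfill the requirements for study completion and are not followed-up outside of the hospital". Inclusion criterion 6 asks only: "Is there a reasonable expectation that the patient will remain in the hospital setting for at least 7 days".
- **Release.** A patient whose dermatitis has healed and who is no longer incontinent, or whose skin is no longer exposed, leaves early: "the patient will be released from the study irrespective of allocation group".
- **Healed but still incontinent.** "If IAD heals before 21 days and the patient is still incontinent, the patient will stay in the study".
- **Withdrawal.** Section 9.3 lists deep pressure ulcer or deep tissue injury, infection or another condition needing topical treatment, and investigator opinion.

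Other safety output is planned. Section 18.1.1 names the number and nature of related serious events, and of four further groups of adverse events. Section 6.10 provides individual patient listings. No section mentions patient-days, event rates, time to first event or a summary of observation time by arm. Section 6.8 leaves a statistical analysis plan to be completed before data lock.

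**The concern.** The chance of having at least one event grows with the days on which an event could be recorded. A crude percentage counts a patient seen for a few days the same as one seen for 21. Under section 9.4 enrolment needs only eligibility and signed consent, so a patient who leaves almost at once is also in the denominator.

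One exit route depends partly on healing, which the trial compares between arms. Discharge can also differ between arms by chance. If mean observation differs, part of any gap in the percentages is follow-up and not safety, and a true gap could be narrowed in the same way. A reader who is not given observation days by arm cannot tell which. The results are meant to inform a possible confirmatory trial (section 5.1), so the safety estimates should be interpretable.

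**Working it through.** **Inputs from the documents.** N = 60, allocated 1:1, so 60 / 2 = 30 per arm (section 6.2). Maximum observation is 21 days (section 9.6). The plan gives no adverse event rate, observation time or healing time, so there is no figure of its own to reproduce for endpoint 11.

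**Assumptions.** Daily risk h of 1%, 2% or 3%, equal in both arms and constant over time. SD of observation time 6 days.

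**Step 1. Chance difference in mean observation.** SE = SD × √(2/n) = 6 × √(2/30) = 1.55 days.

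**Step 2. Effect of a 1.5-day difference.** Percentage with an event = 1 − exp(−h × t). Take t = 14.25 and 15.75 days, which is 1.5 days apart around day 15. The sampling SE of the difference is √{[p(1 − p) + q(1 − q)]/30}.

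| h per day | Shorter arm | Longer arm | Shift | Sampling SE |
|---|---|---|---|---|
| 1% | 13.3% | 14.6% | 1.3 points | 8.9 points |
| 2% | 24.8% | 27.0% | 2.2 points | 11.3 points |
| 3% | 34.8% | 37.7% | 2.9 points | 12.4 points |

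At 2% per day the shift is about a fifth of the sampling SE (2.2 / 11.3 = 0.19).

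**Step 3. Could the release rule create the difference?** The rule was simulated with 1,000,000 patients per arm and the same daily event risk in both. Healing times were exponential, with medians of 7 and 14 days, a strong treatment effect. Release required healing and regained continence, with continence regained at a uniform time over days 1 to 21 in a given share of patients. Discharge had a median of either 14 or 200 days (the latter meaning almost none). Ranges cover h from 1% to 3% and both discharge settings.

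| Share regaining continence | Difference in mean observation | Difference in crude percentage |
|---|---|---|
| 10% | 0.1 to 0.2 days | 0.1 to 0.4 points |
| 50% | 0.5 to 1.2 days | 0.5 to 2.1 points |
| 100% | 1.2 to 2.3 days | 1.0 to 4.5 points |

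Across these settings the sampling SE at 30 per arm is about 8 to 13 points.

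**Step 4. Withdrawal on an event.** Section 18.1.1 names pressure ulcers and skin infections in the observed area as collected adverse events. A patient withdrawn for one is already counted when observation stops. In a simulation with h = 1% and 3% per day, and 70% of events leading to withdrawal, the riskier arm was followed for less time (11.5 against 12.6 days) and still showed the higher percentage (32.0% against 12.3%).

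**Step 5. Does the added measure remove the artefact?** In step 3, first events per 100 patient-days at risk came back equal in the two arms within simulation error, for example 2.00 and 2.00 at h = 2%. This relies on a constant daily risk.

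**The case against.** The strongest reply is that nothing shows the arms will be observed for different times. They are randomised under one release rule, and healing alone does not end observation. The study has no hypothesis, significance level or pass/fail criterion (sections 5.2, 6.3, 6.5). It is descriptive, and the analysis plan still to come is a normal place for exposure-adjusted safety tables. All of this stands. It is why the point is low priority.

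A second reply also stands. A rate per patient-day is not neutral. The one anticipated device effect, an allergic reaction (section 4.2), need not build up evenly over the stay. If events cluster early, the rate would make the arm observed for less time look worse. The rate should therefore not be shown alone.

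Stronger readings are tempting, but the documents do not support them:

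- A reader might infer a bias of about 9 points, as 12 against 18 days would give at 2% per day (1 − 0.98^12 = 21.5%; 1 − 0.98^18 = 30.5%). No section suggests a 6-day gap. It is nearly four of the chance SEs in step 1 (6 / 1.55 = 3.9), and even 9 points is below the sampling SE of 11.3.
- A reader might infer that withdrawal for infection or severe ulcer distorts the percentage. Step 4 shows that it does not for the any-event figure. It does stop observation of later events of other types, and exits on investigator opinion need not follow an event.
- A reader might infer that the percentage is the only planned safety output. Sections 18.1.1 and 6.10 show otherwise.

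**Conclusion.** The point holds in conditional form. Endpoint 11 is a crude percentage over all enrolled patients, observation runs from a few days to 21, and no summary of observation time is planned. Should the arms differ in observation time, the longer-observed arm would tend to show a higher percentage at equal daily risk. The expected size is about 1 to 3 points for a 1.5-day difference (about 2 at 2% per day), and 0.1 to 2.1 points from the release rule if 10% to 50% regain continence. Both are small beside a sampling SE of roughly 8 to 13 points.

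These sizes rest on assumed event risks, an assumed SD, assumed healing and discharge times, and a constant daily risk. The documents do not establish that the arms will be observed for different times or that endpoint 11 will be biased. This is a cheap improvement to reporting, of low priority.

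**What to change.** Keep the planned percentages and counts. In the statistical analysis plan, add to the adverse event table, by arm, overall and for skin-area events:

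1. total patient-days observed;
2. first events per 100 patient-days with an exact confidence interval, counting days only up to the first event or exit;
3. the percentage with an event by Day 07, estimated as the cumulative incidence of first event so that patients who leave earlier contribute the days they were observed.

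Day 07 suits a fixed window because inclusion criterion 6 expects a stay of at least 7 days.

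Confirm that adverse event onset date is a field in the eCRF; the protocol does not say so. Exit dates should be recoverable, since section 9.3 documents the date of withdrawal or discontinuation and section 11.2 has the diary kept daily.

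The cost is a few table columns, with no new visits or patients. The downside is that the rate assumes a roughly constant risk and can mislead if events cluster early, so items 2 and 3 should be read together.
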